5.1. Study Type & Design & Schedule

STUDY TYPE

Multi-centre prospective double-blind placebo-controlled randomized trial

METHODS

Patients will be identified through the Gynaecology 2 Unit outpatient clinic at the RWH, the Endosurgery Gynaecology clinics at the Mercy hospital for women, and associated private practices in Victoria. Referrals and patient histories will be screened by a specialist gynaecologist, fellow trainee or research assistant prior to clinic to identify potential participants. The study will be explained to potential participants. Patients who give their consent will be blindly randomized to receive either PEA/PLD 400 mg/40 mg or placebo. Following randomization, all participants will be asked to complete a NECST questionnaire including a set of pain VAS scales, Quality of life tool (see details in Study methodology). The same questionnaire, with additional questions regarding adverse side effects and treatment compliance, will then be filled 8 weeks later (still before surgery), and 4 months' after surgery. The questionnaire will be available online and as hard copy.

Surgery will then take place as planned with surgical samples for immunohistochemistry and RNA taken only from the Royal Women's Hospital recruited patients. Samples will be collected as described in "Study methodology".

A total number of 260 patients will be recruited, 130 in each arm.

STUDY TABLE

Study Name: Palmitoylethanolamide and polydatin effect on pain and dysmenorrhea in women scheduled for laparoscopic treatment of possible endometriosis: a double blind randomised controlled trial

Protocol Number: 1 Version 0.5, dated 29 September 2020

Assessment/Procedure	Recruitment	After 8 weeks of treatment (pre surgery)	day of surgery	4 months' After surgery
Informed Consent	x			
Baseline Questionnaire	x			
Follow up questionnaire		x		x
Laparoscopy tissue collection (endometrium, endometriosis, blood and peritoneal fluids at RWH only) and Surgeon report			x	

Study Name: Palmitoylethanolamide and polydatin effect on pain and dysmenorrhea in women scheduled for laparoscopic treatment of possible endometriosis: a double blind randomised controlled trial

Protocol Number: 1 Version 0.5, dated 29 September 2020

5.2. Standard Care and Additional to Standard Care Procedures

Standard Care Procedures		Additional to Standard Care		
Procedure	Time/Visit	Procedure	Time/Visit	Dosage
Consultation to book laparoscopy	Prior to recruitment	Questionnaires	At recruitment/ pre-operative	
Laparoscopy +/- treatment of endometriosis if present	As planned by treating gynaecologist	Treatment by either PEA/PLD or placebo	8-10 weeks prior to surgery for 8 weeks	400mg/40 mg
		Questionnaires	After 8 weeks of treatment (pre surgery)	
		Surgery	Fresh tissue samples (endometrium, endometriosis), blood and peritoneal fluids at RWH only	
		Operation questionnaire for surgeon	At operation	
		Questionnaires	4 months' After surgery	

5.3. Randomisation

Block randomization will be performed using the statistical software “R”, directing subjects to treatment with 400mg/40mg PEA/PLD twice daily or placebo of identical appearance. Blocks will consist of 4 subjects who consecutively enter the trial.

Randomization will be stratified based on recruitment site (Royal Women’s Hospital, Mercy Hospital for Women and Private Setting), with lists produced for each site. These will be held by the dispensing compounding pharmacy that will provide the PEA or placebo in identical containers directly to the patients. The subject and medical staff will be blinded to each subject’s treatment.

Study Name: Palmitoylethanolamide and polydatin effect on pain and dysmenorrhea in women scheduled for laparoscopic treatment of possible endometriosis: a double blind randomised controlled trial

Protocol Number: 1 Version 0.5, dated 29 September 2020

5.4. Study methodology

All subjects will be given oral and written information about the study and informed written consent will be obtained by our Research Nurses / Assistant (see attached patient information and consent forms). After consent has been obtained, an initial questionnaire will be completed by the women. The questionnaire includes demographic details, medical background, pain questions about menstrual pain and other pelvic pain symptoms including dysmenorrhoea, deep dyspareunia, dyschesia, daily pain and quality of life assessment.

Quality of life domains will include physical and mental health.

Recruited patients will then be blindly randomized to receive either PEA/PLD 400 mg/40 mg or placebo twice daily for 8 weeks.

Treatment will be prepared by a specialist compounding pharmacy in the form of similar capsules for PEA/PLD and placebo, distributed in similar containers with their content only known to the pharmacists.

The same questionnaire (without the demographic and medical history part) will then be filled at the end of 8 weeks of treatment (still before surgery) with additional adverse drug side effects and treatment compliance assessment.

Surgery will take place within 2 weeks of finishing the study treatment.

Final questionnaire will be sent to participants 4 months' after the surgery to evaluate pain and quality of life.

Collection of tissue Samples and clinical/medical Information

Only patients operated on at the Royal Women's Hospital will be consented for tissue/ biofluid collection. Patients operated at the Mercy Hospital for Women or private hospitals will have their surgeries as planned without any other surgical intervention.

Blood: During surgery, blood samples (25-50 mls, or 1¼ -2½ tablespoons) will be drawn and processed in the laboratories at the RWH.

Endometrial Biopsy: A routine endometrial biopsy will be collected from each woman. The biopsy will be collected following collection of a clinical biopsy during hysteroscopy (endometrial biopsies will only be collected from women providing clinical consent for an endometrial biopsy as part of her planned medical procedure). Endometrial samples will be histologically assessed for cycle stage and some will be stored in RNA later (Life Technologies) for mRNA (NGS analysis) or protein expression studies or used immediately in in vitro cell culture studies.

Endometriotic lesions/cysts and peritoneal tissue: Two small samples of endometriotic lesion tissue will be taken by scissors (not diathermy) as fresh tissue and 1) stored in RNALater for RNA extraction (NGS analysis) and 2) stored in tissue media on ice for immediate in vitro cell culture studies. The formalin fixed lesions sample(s) collected as part of the routine histopathology process and diagnosis, will be accessed for research following routine histopathology assessment.

All other endometriosis lesions will be excised routinely by monopolar diathermy and submitted for routine histopathology. Paraffin embedded ectopic endometrium or peritoneum will only be recalled from pathology following completion of histopathological review (i.e. excess to pathology diagnostic requirements).

Peritoneal Fluid: a sample of peritoneal fluid (up to 10 ml) will be removed for research purposes and frozen for later use. If peritoneal fluid is not found, a saline light wash of

Study Name: Palmitoylethanolamide and polydatin effect on pain and dysmenorrhea in women scheduled for laparoscopic treatment of possible endometriosis: a double blind randomised controlled trial

Protocol Number: 1 Version 0.5, dated 29 September 2020

the pelvis will be done. This does not pose any additional risk for the patient except for extending surgical time by another 1-2 minutes. Samples will be stored at -80°C.

If no active endometriosis is seen, a small biopsy for histological assessment, immunohistochemistry and RNA analysis will be taken by scissors from one of the utero-sacral ligaments.

Surgeons will complete a dedicated operation report on surgical findings immediately after surgery, staging the endometriosis based on the revised American Society for Reproductive Medicine classification of endometriosis (rASRM).

Surgery and post-operative care will otherwise be unaffected by participation in the study. All surgeons and study investigators will be blinded to the patient's allocation to treatment or placebo groups.

Patients will be asked to complete a repeat questionnaire at 4 months' time after surgery.

Tissue bank samples: Endometriotic lesions and endometrium will be stored in RNALater for molecular analysis and/or formalin fixed for routine pathology. Tissues will be stored in the research precinct or recalled from pathology.

Menstrual cycle stage will be determined by pathology.

All data will be collated into REDCap database, which is a secure, web-based application for building and managing complex data currently hosted at the University of Melbourne. Only coded data will be included in the RedCap database; no identifying information will be added.

Study Timeframe

Women scheduled to undergo laparoscopy for suspected endometriosis will be recruited from gynaecology outpatient clinics and prior to surgery at the Royal Women's Hospital, Melbourne (80 patients / year), the Mercy Hospital for Women (50 patients / year) and private rooms. We aim to collect approximately 130 samples per year. This number presumes average surgical volumes of laparoscopy for pelvic pain for suspected endometriosis, accounting for a 30% non-participation rate in eligible participants at each site. Recruitment should take approximately 2 years.

Data analysis and write up will take approximately 12 months.

Total 3 years after recruitment begins to complete the study.

[figure not shown]
6. Study Population

6.1. Recruitment Procedure

As this clinical trial is part of a suite of projects under the umbrella of 'Improving diagnosis and treatment of endometriosis', resources for recruitment will be streamlined together. Eligible participants will be identified to be approached and recruited in a number of ways (Figure 1). Advertising poster, flyer and booklet describing all nine projects (of which this clinical trial is one) will be available in waiting rooms of participating hospital clinics and private gynaecologists' rooms. A website will also be set up through Jean Hailes for Women's Health, a national not-for-profit organisation dedicated to improving women's health.

Participants may be approached to be recruited by a gynaecologist, gynaecology trainee/resident or appointed research nurse/assistant associated with the participating unit. Eligible participants could be approached in the gynaecology outpatient clinic; surgical preadmission clinic; preoperatively on the day of surgery or preoperatively over the phone; over the phone after suitable participants are identified via medical records or if patients have provided their details on the flyer to be contacted.

Figure 1: Recruitment Procedure

Study Name: Palmitoylethanolamide and polydatin effect on pain and dysmenorrhea in women scheduled for laparoscopic treatment of possible endometriosis: a double blind randomised controlled trial

Protocol Number: 1 Version 0.5, dated 29 September 2020

6.2. Inclusion Criteria

- 6.2.1. women aged 18 - 45 with pelvic pain scheduled for laparoscopic treatment of possible endometriosis. Both women with and without previous evidence of endometriosis on ultrasound or previous surgery are eligible
- 6.2.2. women who agree to use any type of contraception and avoid conceiving during the 8-week treatment phase.
- 6.2.3. English speakers

6.3. Exclusion Criteria

- 6.3.1. Pregnancy or actively trying to conceive
- 6.3.2. Breastfeeding
- 6.3.3. Previous hysterectomy
- 6.3.4. Suspected malignancy
- 6.3.5. Inability to provide informed consent

6.4. Consent

The recruiting member of the research team will explain the study to the potential participant, answer questions and provide the participant information. Patients who agree to participate in the study will be contacted by the Research assistant over the phone to receive the consent form either in hardcopy or electronically as per the participant's preference. Consented participants will be allocated a unique trial number.

7. Participant Safety and Withdrawal

7.1. Risk Management and Safety

Safety of PEA/PLD

The tolerability of the drug was viewed in a meta-analysis of all randomized, controlled trials involving the effect of PEA on pain score of different chronic pain conditions (34). Adverse events reported with PEA treatment in 786 patients included gastrointestinal upset (2), drowsiness (1), and heart palpitations (1).

No significant adverse side effects were reported in other studies. Moreover, treatment was given to patients seeking fertility, after surgical diagnosis of endometriosis while trying to conceive with no concern of teratogenicity (35).

Worldwide, more than 800,000 patients have been treated with PEA, most of them in Italy and Spain, with some in The Netherlands, Germany, UK, Canada and the US, and no serious side effects have been reported (36)

Treatment adverse reactions will be tracked by questionnaire. In case of any adverse reaction, patient can stop treatment at any time and seek advice with the allocated contact person for complaints in each hospital or 24 hours a day at the emergency department of each hospital for severe reactions.

Study Name: Palmitoylethanolamide and polydatin effect on pain and dysmenorrhea in women scheduled for laparoscopic treatment of possible endometriosis: a double blind randomised controlled trial

Protocol Number: 1 Version 0.5, dated 29 September 2020

As the PEA/PLD supplement has not yet been definitively proven to be non-teratogenic, patients participating in the study will be requested to avoid conceiving until after treatment and surgery. Participants not using contraception will be required to undergo a pregnancy test prior to commencing the research project.

We recognize that the study treatment and questionnaires may cause distress for some participants. Therefore, we have in place the following actions:

1. In the Patient Information and Consent Form (PICF) participants will be directed to contact a member of the research team (see list below of sites and contact persons) if they identify that they are experiencing distress as a result of participation in the study. The contact for Lifeline is also provided in this document.

Site	Contact Person
Epworth Hospitals	Gynaecology 2 Unit Fellow (RWH)
Mercy Hospital for Women (MHW)	Endosurgery Fellow
Royal Women's Hospital (RWH)	Gynaecology 2 Unit Fellow
Frances Perry House	Gynaecology 2 Unit Fellow (RWH)
Cabrini Malvern	[name]
Holmesglen Private	[name]
St Vincent's Private	[name]
Warringal Hospital	[name]
Sandringham Hospital	[name]

2. This member of the research team will identify the nature and severity of the distress and will determine further action(s) which may include:
 - a. Review in the gynaecology clinic with the involved consultant gynaecologist
 - b. Referral to psychology/psychiatry services at the Mercy Hospital for Women, Royal Women's Hospital or in the local community, as appropriate
 - c. Linking the participant with the hospital consumer advocate
 - d. Linking the patient into appropriate care at their home hospital site if not from the Mercy Hospital for Women or the Royal Women's Hospital
 - e. Organize acute mental health assessment by the Crisis Assessment and Treatment (CAT) team

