7.2. Handling of Withdrawals

Should a participant choose to withdraw from the study no further information will be collected. If the participant withdraws prior completing 6 weeks of medical treatment, she will be removed from the study.

If the participant withdraws following the medical treatment and the second questionnaire but either prior to or after surgery, she will be asked if the data collected prior to their withdrawal is able to be used. Should they decline the data will be removed from the data bank and stored in a separate folder to ensure it is not included in the final analysis.

If the participant falls pregnant during the medical treatment phase, she will be removed from the study.

If the participant falls pregnant after the medical treatment phase and the surgery but prior the last questionnaire she will remain in the study and complete the last questionnaire as planned.

If participants have consumed less than 80% of the treatment, they will be removed from the study.

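### Side effects are first asked about at week 8 and no step records reactions reported during dosing, so reactions that made women leave early can be missing from outcome 4.3.10

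*Protocol*

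**What the plan says.** Assessing the side effects of PEA/PLD is secondary outcome 4.3.10. The method is set in section 7.1: "Treatment adverse reactions will be tracked by questionnaire".

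The side-effect items are not on the baseline form. Section 5.1 has the questionnaire, "with additional questions regarding adverse side effects and treatment compliance, will then be filled 8 weeks later (still before surgery"), and again 4 months after surgery. Section 5.4 agrees on the first date: the form is "filled at the end of 8 weeks of treatment (still before surgery) with additional adverse drug side effects and treatment compliance assessment". It describes the last form as one sent "after the surgery to evaluate pain and quality of life". The study table in 5.1 shows no contact between recruitment and the week-8 form.

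For a reaction during dosing, 7.1 lets the woman stop treatment and "seek advice with the allocated contact person for complaints in each hospital or 24 hours a day at the emergency department". The same section recognises that the study treatment may cause distress. It has a research team member establish the nature and severity of that distress and decide on action, which may include review by the consultant gynaecologist.

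Section 7.2 sets the rules for leaving: "Should a participant choose to withdraw from the study no further information will be collected". It adds: "If the participant withdraws prior completing 6 weeks of medical treatment, she will be removed from the study". Women who took under 80% of the treatment, or who became pregnant while on it, are removed as well. The question whether data already collected may be used is put to women who withdraw after treatment and the second questionnaire. Section 7.3 continues recruitment until each group has 130 women for the primary outcome.

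On data handling, 5.4 states: "All data will be collated into REDCap database".

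**The concern.** These rules work in sequence. Side effects are first asked about when dosing is over. A woman who withdraws earlier never reaches that form, and after withdrawal nothing more may be collected from her. If she telephoned a contact person before leaving, she receives advice, but the protocol states no step that enters her reaction in the database. If she left before 6 weeks she is also removed.

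The losses are therefore selective. Reactions bad enough to make a woman leave say most about tolerability, and they are the ones most likely to be absent. The 4.3.10 comparison would rest mainly on women who tolerated the capsules well enough to stay.

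**Working it through.** The point disputes no figure in the plan. The check sets the rules side by side and then asks how many women could be affected.

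**Timing.** Eight weeks is 56 days. The 6-week threshold falls at 42/56 = 75% of the course. A reaction on day 1 waits 56 − 1 = 55 days for the first form. With full dosing, 80% consumption is reached at 0.8 × 56 = 44.8 days, or 0.8 × 112 = 89.6 of the 112 twice-daily doses.

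**What happens to each woman under 5.1, 5.4 and 7.2**

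| Situation | Week-8 form | Removed | Asked about use of earlier data |
|---|---|---|---|
| Withdraws before 6 weeks | No | Yes | Not stated |
| Withdraws between 6 weeks and the form | No | Not stated, unless under 80% taken | Not stated |
| Stops capsules under 80%, does not withdraw | Possible | Yes | Not stated |
| Withdraws after the form | Yes | Not on this ground | Yes |

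In the first two rows no side-effect question is ever asked. In the third row the form may exist, but 7.2 does not say whether its side-effect answers are kept. The 4-month form does not help in the first two rows, whichever description of its content is right, because it falls after withdrawal.

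**The documents' own count.** Section 7.1 reports gastrointestinal upset (2), drowsiness (1) and palpitations (1) among 786 patients on PEA. That is 2 + 1 + 1 = 4 events, and 4/786 = 0.51%. If every such woman left early, the loss would be 130 × 4/786 = 0.66 women per 130. This count is for PEA, not the PEA/PLD combination.

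**Assumed range.** The documents give no rate of reaction-related withdrawal for the combination. Let r be the share of an arm that withdraws before 6 weeks because of a reaction. If removed women are replaced until 130 remain, the number absent is 130/(1 − r) − 130. If 130 are randomised without replacement, it is 130 × r.

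| Assumed r | With replacement | Without replacement |
|---|---|---|
| 1% | 131.3 − 130 = 1.3 | 1.3 |
| 3% | 134.0 − 130 = 4.0 | 3.9 |
| 5% | 136.8 − 130 = 6.8 | 6.5 |

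So about 1 to 7 women per arm would be absent, whichever way 7.3 is read.

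**Direction.** If the true reaction rate is p, a fraction f of affected women leave and drop out of the table, and the others stay, the observed rate is p(1 − f)/(1 − pf), which is below p. As an illustration with assumed figures, take p = 10% on active, 4% on placebo and f = 50% in both arms:

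- active: 0.05/0.95 = 5.3%
- placebo: 0.02/0.98 = 2.0%

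The difference falls from 6.0 to 3.2 percentage points. These figures imply reaction-related early withdrawal of 5% and 2%, inside the range above.

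**The case against.** The strongest case against has four parts.

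*Reactions during dosing are not ignored.* A reader might infer that nobody looks at a reaction until week 8. The documents do not support that. Section 7.1 provides contact persons, emergency care, and assessment by a research team member of distress, including distress from the study treatment. That provision is worded for distress rather than for all reactions, and it states no data entry. What stands is that recording is not provided for; individual review exists. Nor does 7.1 say that the questionnaire is the only route. That is an inference from no other route being stated.

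*Removal from the study need not mean deleting safety data.* This is fair. Where 7.2 means data removal it says so, for women who withdraw later and decline use of their data. A reader might infer that recorded side-effect data from early leavers are discarded, but the text does not say this. It is silent either way.

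*The analysis set for side effects belongs in a statistical analysis plan.* In part, yes. But an analysis plan cannot restore reports that were never collected, and the collection and removal rules are fixed here. The modified intention-to-treat approach in 8.2 is not tied to side effects.

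*The numbers may be tiny.* At the documents' own 0.5% they are. A reader might also infer that an empty reaction table would wrongly rule out rates of a few per cent. That would need every reaction to end in withdrawal and 130 women retained per arm, and neither is established. Section 5.1 gives 260 as the total recruited, and 8.1 already allows for 30% drop-out within it.

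**Conclusion.** The point holds in this form. The protocol states no step that records a reaction reported during dosing as trial data. It asks about side effects for the first time at week 8, and it stops collection at withdrawal. Women who leave before 6 weeks or take under 80% are removed with no exception for side-effect data. Reactions that made women leave before week 8 can therefore be missing from 4.3.10.

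The bias runs towards reassurance, provided that women with a reaction are likelier to leave than women without one. The difference between arms shrinks if the share leaving is similar in both. The size cannot be known from the documents: under 1 woman per 130 at the PEA count, and about 1 to 7 per arm at the assumed 1% to 5%. No particular hazard of the product is claimed, and clinical care during dosing is in place. The weakness is in the evidence for one secondary outcome.

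**What to change.** 1. In 7.1, have the existing site contact persons enter every reported reaction in REDCap by study ID on receipt, with date, seriousness and date of last capsule. Serious reactions go to an investigator and to the approving ethics committee. This assumes that the allocated contact person in 7.1 is the one listed for each site in that section.
2. In 7.2, state that removal for withdrawal before 6 weeks, for consumption under 80% or for pregnancy applies to the efficacy analysis only. Side-effect data recorded from any woman who took at least one dose stay in the 4.3.10 tabulation by randomised arm, unless she declines.
3. In 7.2, state that women who stop capsules without withdrawing still complete the week-8 form. A woman who tells the team that she is withdrawing is offered the existing side-effect items, optionally and before the withdrawal takes effect. The rule against collecting anything afterwards is unchanged.

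Reports volunteered during dosing should be tabulated separately from questionnaire answers, because the two are elicited differently.

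The cost is wording in two sections, one form in a database already planned, and a little logging time: at 260 women over about 2 years, 260/24 = 10.8 start per month. No new visit, committee or unblinding is needed. A woman who leaves without telling anyone of a reaction will still not be captured.

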4.3. Outcome Measures

Primary outcomes

- 4.3.1. To compare the change in dysmenorrhoea VAS score between PEA/PLD and placebo treatment in patients with endometriosis prior to laparoscopic surgical treatment.
- 4.3.2. To compare the change in dyspareunia, dyschezia and persistent pelvic pain VAS score between PEA/PLD and placebo treatment in patients with endometriosis prior to laparoscopic surgical treatment.

Secondary outcomes

- 4.3.3. To compare the change in dysmenorrhoea VAS score between PEA/PLD and placebo treatment at baseline and 4 months after laparoscopic surgery for endometriosis.
- 4.3.4. To compare the change in dyspareunia, dyschezia and persistent pelvic pain VAS score between PEA/PLD and placebo treatment at baseline and 4 months after laparoscopic surgery for endometriosis.

Study Name: Palmitoylethanolamide and polydatin effect on pain and dysmenorrhea in women scheduled for laparoscopic treatment of possible endometriosis: a double blind randomised controlled trial

Protocol Number: 1 Version 0.5, dated 29 September 2020

- 4.3.5. To compare the change in dysmenorrhoea, dyspareunia, dyschezia and persistent pelvic pain VAS score between PEA/PLD and placebo, before surgery, in patients without surgical evidence of endometriosis.
- 4.3.6. To compare the change in dysmenorrhoea, dyspareunia, dyschezia and persistent pelvic pain VAS score between PEA/PLD and placebo, at baseline and 4 months after laparoscopic surgery without evidence of endometriosis.
- 4.3.7. To compare the change of quality of life between PEA/PLD and placebo treatment in women with surgical evidence of endometriosis, before surgery and again after surgery.
- 4.3.8. To compare changes in cellular and molecular markers from endometriotic lesions, blood and peritoneal fluid samples between patients treated by PEA/PLD and placebo.
- 4.3.9. To correlate changes in VAS score with changes in cellular and molecular markers, in patients with endometriosis, treated by PEA/PLD and placebo.
- 4.3.10. To assess the side effects of PEA/PLD.

5. Study Design

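### The removal rules in section 7.2 make no exception for the side-effect outcome, so women who stop early for a reaction drop out and each arm's side-effect rate is biased downward

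*Protocol*

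**What the plan says.** Protocol 4.3.10 lists as a secondary outcome: "To assess the side effects of PEA/PLD". Section 7.1 names one means of recording: "Treatment adverse reactions will be tracked by questionnaire". Section 5.4 places the first such questions "at the end of 8 weeks of treatment (still before surgery) with additional adverse drug side effects and treatment compliance assessment". Section 5.1 describes the follow-up form thus: "with additional questions regarding adverse side effects and treatment compliance, will then be filled 8 weeks later (still before surgery), and 4 months' after surgery". In the study table in 5.1, no questionnaire falls between recruitment and week 8.

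On stopping, 7.1 states: "In case of any adverse reaction, patient can stop treatment at any time and seek advice". The sentence goes on to a contact person and the emergency department. It attaches no research record to the event.

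Section 7.2 has three relevant rules:
- "Should a participant choose to withdraw from the study no further information will be collected".
- A woman who withdraws before 6 weeks of treatment is removed.
- "If participants have consumed less than 80% of the treatment, they will be removed from the study".

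None of the three mentions the reason for stopping or makes an exception for the side-effect outcome. Section 7.3 continues recruitment until each group has 130 women for the primary outcome. Section 8.2 names a modified intention-to-treat approach without saying who is in it.

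**The concern.** An adverse reaction is one of the reasons a woman may stop her capsules. If stopping early leads to removal, the chance of being counted depends on whether she had the event that 4.3.10 sets out to count. The women lost are those whose reaction was troublesome enough to make them stop, which is the group a side-effect assessment most needs.

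Replacement under 7.3 can hide the loss. Recruitment goes on until 130 women per group are available for the primary outcome, so the side-effect table may look full while early stoppers are absent from it. The trial could later be cited as placebo-controlled evidence that the product is well tolerated, with rates lowered by its own removal rule.

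**Working it through.** **Plan's own figure.** The protocol states no expected side-effect or discontinuation rate for this trial, so there is none to reproduce. Its only background figure is in 7.1: 2 + 1 + 1 = 4 events in 786 patients given PEA, or 4/786 = 0.5%.

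**When the rules bite.** Sections 5.3 and 5.4 give twice-daily treatment for 8 weeks, which is 56 days and 2 × 56 = 112 doses.
- 80% of treatment: 0.8 × 112 = 89.6, about 90 doses, or 0.8 × 56 = 44.8 days if no dose is missed.
- The 6-week rule: 6/8 = 75% of treatment. A woman who leaves before 6 weeks is therefore below 80% as well.
- First scheduled side-effect question: the end of week 8, day 56.

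A woman who stops for a reaction before about day 45 is thus removed under 7.2, and no side-effect question is scheduled before then.

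**What happens to her data.**
- If she withdraws from the study, nothing further is collected, and no side-effect questionnaire will have been given.
- If she only stops the capsules, she may complete the week-8 form. That form also asks about compliance, which is what the 80% rule needs. She is then removed.
- If she reacts but takes at least 80%, she stays and is counted.

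**Direction and size.** Let p be the true share of women in an arm with a reaction, and s the share of those women who are removed. Both are assumptions. Suppose removal for other reasons is unrelated to reactions. Of N women, Np react, Nps are removed, and N(1 − ps) remain, of whom Np(1 − s) reacted:

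observed rate = p(1 − s) / (1 − ps)

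For p between 0 and 1 this is below p whenever s > 0.

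| True p | s = 10% | s = 25% | s = 50% | s = 75% |
|---|---|---|---|---|
| 5% | 4.5% | 3.8% | 2.6% | 1.3% |
| 10% | 9.1% | 7.7% | 5.3% | 2.7% |
| 20% | 18.4% | 15.8% | 11.1% | 5.9% |

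Worked case, p = 10% and s = 50%: 0.10 × 0.50 / (1 − 0.05) = 0.05/0.95 = 5.3%. Replacement does not change this ratio. It only restores the denominator.

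**Between arms.** Take assumed true rates of 20% on active product and 10% on placebo, a difference of 10 points:
- s = 25% in both arms: 15.8 − 7.7 = 8.1 points.
- s = 50% in both arms: 11.1 − 5.3 = 5.8 points.
- s = 50% active, 25% placebo: 11.1 − 7.7 = 3.4 points.
- s = 75% active, 25% placebo: 5.9 − 7.7 = −1.8 points.

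If p and s are the same in both arms, the true and observed differences are both zero.

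**The case against.** Several stronger readings are tempting, and the protocol does not support them.

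- **That women who stop are never asked about side effects.** The bar on further data in 7.2 applies to withdrawal from the study. Stopping capsules under 7.1 is a different act, and a stopper who has not withdrawn may complete the week-8 form. What stands is that 7.2 still removes her if she took under 80%. Whether removal discards answers already given is not spelled out. Exclusion is the natural reading, but 7.2 describes taking data out of the data bank only for women who decline its use.
- **That only women who tolerated the product are assessed.** Women who react and continue, or who stop after reaching 80%, remain.
- **That a real rate would be reported as zero.** This needs no reaction at all among the women who remain. In the range tabulated, the observed rate never reaches zero.
- **That safety would rest on 130 × 0.7 = 91 women per arm.** The 30% in 8.1 is a general drop-out allowance, not a rate of stopping for reactions, and 7.3 recruits until 130 per group are reached.
- **That the comparison with placebo is biased by a known amount.** The rules are the same in both arms and applied blind. Distortion depends on differences in reaction or stopping rates, which the protocol does not give.

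Two further objections have weight. The protocol's background rate of 0.5% would mean about 130 × 4/786 = 0.7 affected women per 130, so the absolute bias could be small. With events that rare, however, removing one or two women could erase most of the signal. It can also be said that a safety set and discontinuation tables belong in the statistical analysis plan. That is right, and their absence is not the finding. The finding is a stated removal and data-collection rule, and no analysis plan can recover answers that were never collected.

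**Conclusion.** The point holds in a limited form. Read as written, 7.2 removes women for under 80% consumption or for withdrawal before 6 weeks without regard to the reason. Together with 7.1 and a first side-effect question at week 8, this makes removal depend on the outcome in 4.3.10 and biases each arm's side-effect rate downward.

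The direction follows from the rules, provided that some women stop early because of a reaction and that removal means exclusion from the side-effect results. The size does not follow from the protocol. For an assumed true rate of 10%, the observed rate runs from 9.1% to 2.7% as the share of affected women removed goes from 10% to 75%. The effect on the difference from placebo is conditional on the arms differing in reactions or in stopping.

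Severity is should-fix. The outcome is secondary and this point does not bear on the primary pain comparison, but data not collected at the time cannot be recovered.

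**What to change.** Amend the data-handling wording only. No treatment or stopping rule needs to change.

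1. In 7.2, state that the under-80% and under-6-week removals do not apply to the side-effect outcome.
2. In 7.1 and 7.2, separate stopping treatment from withdrawing from the study, so that a woman who stops her capsules stays in follow-up unless she also withdraws.
3. Give the existing side-effect and compliance questions at discontinuation, with the reason for stopping, unless the woman declines.
4. In 8.2, assess side effects in all women who took at least one dose, by product received, and report discontinuations for adverse reactions by arm. The detail can sit in the statistical analysis plan.

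The cost is protocol wording, one additional use of an existing form for women who stop, and a side-effect table that may be less favourable to the product.
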